4.10 Quality Assurance Plan

Data will be collected centrally by our research staff rather than locally at each clinic. Computerized data collection methods (Redcap) optimize quality assurance. Redcap system does not accept outliers, illogical response patterns, etc. The PI will have weekly meetings with the research assistants to discuss qualitative comments received during data collection and any problems in data collection. The statistician will periodically examine the database to look for irregularities. Initial data analyses will examine distributions of variable scores, comparability of baseline characteristics, follow-up rates and use of extra-study cessation treatment across conditions in case analyses need to be adjusted for these.

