Title: TIP TOP (Tobacco Intervention in Primary Care Treatment Opportunities for Providers)**Abstract**

Most smokers do not make a quit attempt in any given year. For those who do, use of evidence-based treatment, including the use of nicotine replacement therapy (NRT) is modest at best. Brief physician advice to quit, based on the 5As/5Rs model, while offering some efficacy, is inconsistently administered and thus has limited population impact. There is a clear need for more efficacious methods, particularly in the clinical setting, to promote quitting. Our team recently completed a large, nationwide clinical trial of NRT sampling, i.e., testing whether brief provision of NRT promotes further uptake of cessation behavior, higher incidence of quit attempts, and higher rates of abstinence. The results of that trial were promising for all outcomes, and suggested that NRT sampling works by increasing both motivation and confidence to quit and increasing familiarity with NRT products as an option for quitting.

NRT sampling, when added to physician advice to quit, is uniquely suited to busy primary care settings for several reasons. First, primary care represents a prominent point of healthcare contact for a large number of smokers. Second, the sampling intervention is simple, takes only a few minutes to deliver, and requires minimal instructions. Third, unlike other clinic-based strategies such as motivational advice, NRT sampling is behaviorally based, and offers providers and patients, both of whom are often frustrated by persuasive messaging, a concrete experience to catalyze quitting. Fourth, sampling is supported by numerous quitline studies that show that free medications significantly increase call volume and cessation. Finally, sampling has a strong theoretical foundation to suggest that brief exposure to a product promotes wider acceptability of it.

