Our **Primary Specific Aim** is to examine cessation outcomes of a large-scale (N=1300; 20 participating clinics) randomized clinical trial of 1) Standard Care, based on established guidelines (Ask, Advise, Refer [quitline referral]) vs. 2) Standard Care + NRT Sampling. Participants will be drawn from a network of primary care settings that has established infrastructure in which to embed clinical research. Randomization will be at the clinic level, but individual participants represent the unit of analysis. Identified smokers who meet eligibility criteria will be consented into a trial. Interventions will be delivered within the primary clinic directly by providers who are trained and monitored on study procedures. All participants will receive advice to quit and referral to state quitlines. Half of the sample will receive a small token bag that includes samples (i.e., 1-2 week starter kit) of both nicotine patch and lozenge. Follow-up assessment (through 6 months) will track both primary (abstinence, quit attempts, use of additional treatment) and secondary (motivation, confidence) outcomes. Our team has strong experience in such trials, including methods to efficiently recruit and effectively retain large numbers of smokers in clinical research. Our principle hypotheses are as follows:

Hypothesis 1a: As compared to Standard Care model of physician-delivered brief advice (Ask, Advise, Refer), provision of brief advice + NRT samples within primary care setting will result in a higher abstinence rates (7-day, point prevalence at 6 month follow-up).

Hypothesis 1b: Brief advice + NRT sampling will result in longer period of abstinence (longest # days non-smoking) across the entire study duration.

Hypothesis 2: NRT sampling will result in higher rates of quit attempts (any self-defined and any 24hr quit attempt).

Hypothesis 3: Brief advice + NRT sampling will result in higher subsequent uptake of evidence-based treatment (behavioral, pharmacological assistance).

NRT sampling represents a brief, concrete, easy to explain strategy that both healthcare providers and smokers readily accept. Thus, it is uniquely suited to the primary care setting, and could be a novel, behaviorally based intervention to promote quitting. If so, NRT sampling holds great significance on both a clinical and policy level.

Human Subjects Research**1. Risks to Human Subjects****1.1 Human Subjects Involvement and Characteristics**

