4.9 Data Analysis Plan

All analyses are based on an intent-to-treat approach, and are nearly identical to analyses from our current and prior studies. Exploratory analysis will be performed on all variables to determine if transformations are needed. Any significant baseline differences between groups will be included in regression analyses described below. All analyses below will be run separately for full intent-to-treat sample (immediately below), per protocol, and, within the NRT group, using those participants who used single vs. combined NRT products.

Examination of Potential Site Differences Outcomes and patient characteristics will be estimated across clinics using summary statistics and confidence intervals. This will be considered an exploratory analysis due to the relatively large number of clinics and, hence, the large number of multiple comparisons that could arise. Grouped logistic regression modeling may be used to describe associations between clinic characteristics and binary clinical outcomes (e.g., quit rate).

Missing Data & Dropout The most conservative approach for handling missing data is to substitute them with baseline values, assuming outcomes have all returned to baseline, with no quit attempts made or abstinence achieved. If this assumption is incorrect, it biases the results towards the null by reducing between group differences. Since we expect few missing data, we will use this approach. If missing data >10%, we will calculate results using this conservative method but also using methods in which missing data are imputed as described in the SRNT guidelines. We will also assess whether dropout is differential by study group. In our current and recent studies of cessation induction, this has not been the case. Abstinence will be reported both with and without (missing samples) cotinine verification.

Hypotheses 1a, 2, & 3 These hypotheses predict that provision of NRT samples will lead to higher abstinence rates (Hyp. 1a), incidence of quit attempts (Hyp. 2), and uptake of additional treatment (Hyp. 3). Logistic regressions will be performed for each outcome with treatment group (standard care vs. NRT sampling)

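### Section 4.10 leaves open adjusting analyses for use of extra-study cessation treatment, which is the Hypothesis 3 outcome; section 4.9 does not rule this out

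*Combined protocol and SAP*

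**What the plan says.** Section 4.10 closes with a list of early data checks. Besides variable distributions and baseline comparability, the statistician will look at "follow-up rates and use of extra-study cessation treatment across conditions in case analyses need to be adjusted for these". The sentence names no analysis, sets no threshold and exempts no outcome.

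The Specific Aims make treatment use an outcome of the trial. Hypothesis 3 reads: "Brief advice + NRT sampling will result in higher subsequent uptake of evidence-based treatment (behavioral, pharmacological assistance"). The same section says follow-up will track "primary (abstinence, quit attempts, use of additional treatment") outcomes, so additional treatment is listed beside abstinence as primary.

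Section 4.9 sets out the models. "All analyses are based on an intent-to-treat approach". For Hypotheses 1a, 2 and 3, "Logistic regressions will be performed for each outcome with treatment group (standard care vs. NRT sampling") as the covariate, fitted by GEE for clustering within clinic. The group coefficient is tested by a Wald test at one-sided 0.025. On adjustment: "Any significant baseline differences between groups will be included in regression analyses described below". Further models take in covariates such as age, gender and race. Dropout is compared by arm under Missing Data & Dropout in the same section, where missing values are set to baseline and imputation is added if more than 10% are missing.

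**The concern.** Of the quantities that 4.10 compares across arms with adjustment in mind, baseline characteristics are measured before the intervention. Use of extra-study treatment is not, and the trial predicts that sampling will change it.

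The trial asks whether adding samples to standard care raises quitting overall. That includes quitting that comes about because the sample led a patient to obtain more treatment. An abstinence model that holds later treatment fixed estimates only the part of the effect that does not pass through it. It also conditions on a variable that probably shares causes with quitting, motivation being the obvious one, so the adjusted coefficient is not a clean direct effect either. The same applies to longest abstinence (Hypothesis 1b) and quit attempts (Hypothesis 2). In the Hypothesis 3 model the covariate would be essentially the outcome.

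The option would be exercised after arm differences had been seen. A difference in treatment use is what Hypothesis 3 predicts, so the adjustment would look most attractive when the intervention was working as intended.

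**Working it through.** The plan gives no figure on this point, so there is none to reproduce. The check has two parts.

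**Reading the sections together.** Section 4.9 specifies group-only models and names only baseline covariates as additions. Treatment uptake appears there only as an outcome. Section 4.10 opens a route to adjust for it, and neither section says which governs. The documents draw no distinction between extra-study cessation treatment (4.10) and additional treatment (Specific Aims). Treatment beyond the supplied samples is the natural reading of both.

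**Illustrating the size.** One input comes from the documents: control abstinence of 15%, the projected base rate in sections 2.2.5 and 4.13(a). The rest are assumptions:

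- uptake of 20% in control, and u1 = 25% to 40% with sampling
- odds ratio of abstinence for users against non-users, U = 2 or 3
- direct odds ratio of sampling at fixed uptake, D = 1.0, 1.2 or 1.4

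Model: logit P(abstinent) = a + ln(D) × arm + ln(U) × uptake, where expit is the inverse logit.

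1. Choose a so that 0.80 × expit(a) + 0.20 × expit(a + ln U) = 0.15.
2. Sampling-arm rate p1 = (1 − u1) × expit(a + ln D) + u1 × expit(a + ln D + ln U).
3. Total OR = [p1/(1 − p1)] / (0.15/0.85).
4. The uptake-adjusted OR is D. Share of the effect lost = 1 − ln(D)/ln(total OR).

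Worked case with U = 3, u1 = 35%, D = 1.2:

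- Control: 11.66% of non-users and 28.36% of users abstinent; 0.80 × 0.1166 + 0.20 × 0.2836 = 0.150.
- Sampling: 13.67% and 32.21%; p1 = 0.65 × 0.1367 + 0.35 × 0.3221 = 0.2016.
- Total OR = (0.2016/0.7984)/(0.15/0.85) = 1.43.
- Share lost = 1 − 0.182/0.358 = 49%.

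| U | u1 | D (adjusted OR) | p1 | Total OR | Share lost |
|---|---|---|---|---|---|
| 2 | 25% | 1.4 | 20.4% | 1.45 | 9% |
| 2 | 25% | 1.2 | 18.0% | 1.24 | 16% |
| 2 | 30% | 1.4 | 21.0% | 1.50 | 17% |
| 2 | 30% | 1.2 | 18.6% | 1.29 | 29% |
| 3 | 35% | 1.2 | 20.2% | 1.43 | 49% |
| 3 | 40% | 1.2 | 21.1% | 1.51 | 56% |
| 3 | 35% | 1.0 | 17.5% | 1.20 | 100% |

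**Cross-check on power under different assumptions.** Take 650 per arm (half of 1300), abstinence of 15% against an assumed 21%, one-sided 0.025, and ignore clustering. The unadjusted OR is 1.51 with power of about 0.80. After adjustment for uptake:

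- uptake 20% vs 25%, doubling abstinence: OR 1.45, power 0.72
- uptake 15% vs 25%, doubling abstinence: OR 1.39, power 0.60
- uptake 15% vs 30%, tripling abstinence: OR 1.21, power 0.23

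These show direction and spread. They are not the trial's power, which clinic-level randomisation would lower.

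**The case against.** The strongest reply is that section 4.9 already fixes the confirmatory model: group as the covariate, a stated test and level, intent to treat, baseline covariates only. Section 4.10 concerns quality assurance, and its sentence describes initial checks, made in case adjustment proves necessary. This largely stands. A reader might infer that 4.10 is a rule that fires when the arms differ, or that the primary abstinence test will be replaced by an adjusted one. The text supports neither: it has no trigger, names no model and commits to nothing. What remains is an open option that 4.9 does not close.

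A second reply concerns mechanism. The documents do not name later treatment use as a mediator of abstinence. The Abstract's remark about "increasing familiarity with NRT products as an option for quitting" summarises the completed earlier trial, as does its account of sampling promoting further uptake. That uptake carries part of the effect is therefore an inference, though a natural one: sections 1.3.5 and 4.15.5 say that pharmacotherapy in smokers not wanting to quit promotes cessation. The Hypothesis 3 problem, an outcome conditioned on itself, does not depend on it.

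A third reply concerns follow-up rates, which sit in the same sentence. A reader might extend the argument to them. It does not extend: follow-up is also observed after the intervention, but it is not a hypothesised outcome, and section 4.9 already treats differential dropout as a missing-data question.

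**Conclusion.** The concern holds in limited form. Section 4.10 permits, without requiring, adjustment of unspecified analyses for a post-intervention variable that is itself the Hypothesis 3 outcome, and 4.9 does not exclude it. Used for Hypotheses 1a, 1b or 2, the adjustment would generally attenuate the total effect of sampling if sampling raises uptake and uptake raises quitting. Used for Hypothesis 3, it would condition on the outcome.

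The direction is supported but the size is not. The 9-56% range rests on assumed uptake and odds ratios; only the 15% base rate is the plan's. It also assumes no common causes of uptake and quitting, and the same direct effect in users and non-users. A reader might conclude that adjustment would erase the trial's effect. That follows only if sampling has no direct effect at all, which the documents do not say.

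Because the specified main models leave the variable out, this is a change that should be made rather than a flaw in the primary analysis as written.

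**What to change.** In section 4.10, take use of extra-study cessation treatment out of the variables for which analyses may be adjusted, and add a statement such as: *The models in section 4.9 govern. Only variables measured before the intervention may enter the models for Hypotheses 1a, 1b, 2 and 3. Treatment obtained outside the study is reported by arm as the Hypothesis 3 outcome. Any analysis of its role in abstinence is a mediation analysis, labelled exploratory.*

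As a separate edit, have 4.10 refer differences in follow-up between arms to the Missing Data & Dropout methods in 4.9 rather than to covariate adjustment.

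The cost is a few sentences. No new data, visits or staff are needed, and the comparison of treatment use by arm is still made.

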4.11 Reporting mechanisms of AEs/SAEs to IRB, FDA, NIDA

Prior to the start of the study, the protocol will be registered on the clinicaltrials.gov registry. In our prior work on smoking reduction, in which smokers were using OTC NRT for non-cessation indications, we three times filed for an IND with FDA. On all three occasions the FDA has stated an IND is not necessary. For this study, we do not believe an IND is necessary, but we will again notify FDA of our intent to conduct a trial with a non-approved indication.

Serious Adverse Events (SAEs) are defined as any even that is fatal or life threatening, is permanently or significantly disabling (physically or psychologically), requires inpatient hospitalization or prolongation of hospitalization, contributes to a congenital anomaly/birth defect or is any medical event that requires treatment to prevent one of the medical outcomes listed above.

For a study of this size (N=1300) and duration (6 months), we do expect some deaths to naturally occur, all of which will be reported to IRB, but given that we are providing a mere 2-week sample of NRT, we do not anticipate any study-related SAEs. In our ongoing trial of now 1200 smokers followed for 1 year, there have been <5 deaths total.

All serious AEs (SAEs), study related or not, will be reported to the MUSC Committee on Human Research within 72 hrs. We will also report SAEs to NIDA within 72hrs of learning of any such occurrence, using the NIDA SAE Report Form. Follow-up of all unexpected and serious AEs will also be reported. All AEs are reviewed weekly by the PI and yearly by the IRB. Any significant actions taken by the local IRB, protocol changes will be relayed to the funding agency. We estimate the significant AE rate to be 5% or less. If the monthly monitoring indicates the rate is above this, we will convene a special meeting of the DSMB.

4.12 Reporting mechanisms of IRB actions to NIDA & Report of changes or amendments to the protocol

We anticipate numerous amendments to our IRB protocol as new clinics are brought online into recruitment (all new personnel will need IRB approval). We also anticipate minor procedural amendments (e.g., updates of assessment protocol). We will not update NIDA for each individual minor amendment, but we will a) discuss with NIDA in advance any need for major protocol changes (e.g., change in clinics, significant (+/-10%) change in sample size), and b) provide IRB approval to NIDA once these major protocol changes have been local approved. We will report any IRB-actions within 5 business days. Notice of annual continuing approval will be included within each annual progress report to NIDA.

4.13 Trial stopping rules

There are three potential reasons to stop the trial prematurely: a) undermining of cessation, b) higher-than-anticipated quit rates, and c) significant rate of adverse events. Each is addressed below.

a) To protect against undermining of cessation, we will form a Data Safety and Monitoring Board (DSMB) and have them conduct an interim analysis after 50% of the sample has completed 6 month follow-up. We chose this number as this is the minimum necessary given our base rate is projected to be 15% and one has to see clear trend toward an even lower rate. To do this, the statistician will provide a copy of the dataset to the board. If this occurs, this board will independently decide on whether to stop the study.

b) We plan to examine the data halfway through enrollment to determine if observed differences in quit rates are so large that the trial should be stopped early. Using the method of O'Brien and Fleming (129) the significance level for this interim analysis is $\alpha = 0.005$. According to this same reference, conducting this analysis decreases our power for detecting our projected differences only from 0.80 to 0.79.

c) The research staff will report any unexpected AEs or any scores of "severe" on the side-effect symptom rating form or any FDA-defined serious AEs to the PI within 24 hrs so that the PI can decide on the appropriate action. All unexpected AEs will be monitored while they are active to determine if treatment is needed. Since a maximum two week supply of OTC nicotine lozenge and patch will be provided, adverse events will be rare. Nonetheless, they will be coded on a weekly basis using the FDA's COSTART rules (127) and entered into a database. For each weekly study meeting, the research assistants will prepare a summary of all AEs, including their severity, whether they occurred during smoking or abstinence, caused a dropout, required treatment and presumed relation to drug intake. The PI will review this at the weekly study meeting (or before if more urgent). At the weekly meeting (or before if urgent), research assistants will report any premonitory symptoms of emergence of a mental disorder such as depression or alcohol dependence. [name], a board-certified psychiatrist, will be available for on-site medical supervision. Any study-related SAE will be reported to the DSMB immediately, which may convene a special meeting. Aggregate summary of all AEs will be provided at each regularly scheduled DSMB meeting.

4.14 Conflicts of Interest

The Medical University of South Carolina is fully compliant with federal laws in reporting of conflicts of interest. All key personnel listed within this application have complied with this policy. Any conflicts of interest will be acknowledged in any publications or conference proceedings.

4.15 Potential risks and benefits to participants

The research protocol calls for non-treatment seeking smokers, who will vary across the motivational spectrum from wanting to quit vs. not wanting to quit, to receive standard care (Ask, Advise, Refer) or NRT sampling. The sampling intervention consists of a two-week supply of both nicotine patch and lozenge, both over-the-counter products that have received extensive support for their efficacy and safety (22, 107-112). Nonetheless, there are potential for risks for each product alone, as well as when used concurrently. We believe these risks, described below, will be minimal and mild.

4.15.1 Nicotine lozenge In a prior trial of the particular lozenge we will be using, 68% and 71% of 2 and 4 mg users of nicotine lozenge reported an adverse event (AE) vs. 54% of placebo users (113, 114). With both active doses of the lozenge, 7% dropped out due to AEs and 7% dropped out due to AEs on placebo. With both active doses, 1.6% reported a serious AE which was not different than that for placebo. There were no deaths or irreversible injuries deemed possibly due to lozenge. The most common AEs were nausea, flatulence and upper respiratory tract infection (113). The current labeling on OTC lozenge states pregnant and breast feeding women, those less than 18 years of age, those using a prescription medication for depression or asthma or a smoking cessation medication and those with heart disease, recent heart attack, irregular heartbeat, high blood pressure not controlled by medication, stomach ulcers or diabetes should consult a provider before using the lozenge.

In a recent trial of placebo vs. single vs. multiple medications for smoking cessation (92), the three most common adverse events within the lozenge group were 1) nausea: 7.8%, compared to 4.4% within placebo group, 2) mouth/throat irritation: 6.7%, compared to 3.3% within placebo group, and 3) hiccups: 6.2%, compared to 0.3% within placebo group. All other adverse events occurred <5%. In our recent trial of sampling nicotine lozenge, which was not placebo-controlled but was based on a similar sampling strategy as proposed here, the most common adverse events were nausea (23% of all adverse events), throat irritation (17%), and hiccups (13%).

Dependence on the lozenge and harm from concurrent use of lozenge and cigarettes has not been reported but has not been studied. The pharmacokinetics of the lozenge most closely matches that of nicotine gum. With gum used for abrupt cessation, the estimated incidence of dependence is 1-3% (115). Although an early anecdotal report suggested concomitant use of NRT and smoking could induce heart attacks, several large empirical studies since then have failed to confirm this observation (116). For example, in the LHS study (117) and in our prior study (48), large numbers of smokers concurrently smoked and used nicotine gum or other NRT products and the incidence of any significant AEs was < 1%.

4.15.2 Nicotine patch The most common side effects from nicotine patch are skin irritation, insomnia, and headache or nausea. In an early but seminal placebo controlled test of patch (118), there were few systemic side effects of patch use: 21% vs. 15% of smokers in the patch and placebo groups respectively reported a side effect during the treatment period. The most frequent symptoms with the patch as compared with the placebo patch were headache (4 vs. 4 percent), nausea (4 vs. 1 percent), and vertigo (4 vs. 0 percent). Transient mild itching was reported by 14% of the subjects in the patch group and 1% in those in the placebo group after the first week ($P<0.001$). At each visit, 4.5% to 7.3% of the remaining subjects in the patch group reported erythema, as compared with 2.3% to 6.7% of those in the placebo group. Acute eczema persisting for several days in the area of the patch caused 1.4% of the subjects in the nicotine group and 0.7% of those in the placebo group to stop using the patch.

In a separate but similar study comparing bupropion vs. patch vs. combined bupropion/patch vs. placebo (119), the most common adverse events reported by patch participants were 1) insomnia (30% in active patch group vs. 20% in placebo), 2) headache (28% in active patch group vs. 33% in placebo), 3) application site reactions (19% in active patch group vs. 7% in placebo), and 4) dream abnormalities (18% in active patch group vs. 3% in placebo).

Finally, in a recent trial of placebo vs. single vs. multiple medications for smoking cessation (92), the two most common adverse events within the patch group were 1) skin irritation: 14.7%, compared to 2.7% within placebo group, and 2) disturbed sleep: 11.3%, compared to 5.6% within placebo group. All other adverse events occurred <5%. Seven percent of patch users vs. 4% of placebo users discontinued medication due to adverse events.

4.15.3 Combined patch & gum Our sampling intervention allows smokers to briefly try evidence-based cessation medications, either singularly or concurrently. We do not explicitly encourage dual use, but we will not discourage it either. We do believe combined medication use is safe. Combination treatments are often suggested for more dependent smokers and/or smokers with chronic medical conditions (120-122). One review in particular (120) provides significant rationale by which combined NRT should not incur significant risks, since NRTs provide lower doses per unit or per hour than are typically obtained by cigarette smoking, and the rate of nicotine administration for all NRT products is substantially slower than that from an inhaled cigarette.

In a recent trial of placebo vs. single vs. multiple medications for smoking cessation (92), the four most common adverse events within the combined patch/lozenge group, were 1) disturbed sleep: 9.0%, compared to 5.6% within placebo group, and 2) skin irritation: 8.9%, compared to 2.7% within placebo group, 3) nausea: 7.9%, compared to 4.4% within placebo group, and 4) mouth/throat irritation: 5.7%, compared to 53.3% within placebo group. All other adverse events occurred <5%.

4.15.4 Combined use of any NRT product and smoking Our study allows smokers to sample individual or combined NRT products, but without a requirement of a formal quit attempt. Thus, smokers could be using NRT products concurrently (same day) as smoking. This could result in nicotine intoxication; i.e. nausea, dizziness, headache, stomachache, etc (116). In our prior study, participants completed a nicotine intoxication scale, and we found no evidence of nicotine intoxication when gum and cigarettes were used concurrently. In addition, our review of prior smoking reduction studies found most participants did not have higher than normal cotinine levels with concurrent use of cigs and NRT, and there were few AEs reported (123).

4.15.5 Undermining Cessation Another potential risk is that the sampling intervention will decrease rather than increase future cessation as briefly discussed in Section A.5. However, the limited data available (124) suggest this is unlikely. Our prior work on providing NRT to smokers not yet fully committed to cessation (47, 48, 67), as well the work of many others (125, 126) clearly demonstrate that use of pharmacotherapy among smokers not wanting to quit effectively promotes cessation.

4.15.6 Confidentiality A final risk is breach of confidentiality.

Benefits: All smokers in this trial will receive at minimum standard care, consisting of brief provider advice to quit and referral to quitting resources. Half of the participants in the trial will receive samples of two products that alone and in combination have shown significant benefits on quitting. Thus, there are direct benefits to all participants. The major benefit to society will be whether a brief sample of evidence-based medication serve as an effective method to catalyze cessation (abstinence, quit attempts, uptake of additional quit resources). The risks of nicotine lozenge and patch are very small, even when used concurrently. The sampling period of our trial consists of two weeks, which further minimizes risk potential. Smoking cessation is the most important activity to improve public health and many smokers are resistant to quitting. Recent trends in smoking cessation are moving towards longer, more intensive treatments that combine behavioral and pharmacologic treatment. While efficacious, such approaches do not lend themselves to clinical practice within primary care settings, where providers have limited resources (time and expertise) to address tobacco dependence. If NRT sampling results in the hypothesized outcomes, it could offer an innovative, easy to implement option that has

significant reach. Thus, NRT sampling represents a significant strategy that offers both clinical and policy significance to promote public health.

